7.3 Treatment – Arm 2: Ipilimumab + Nivolumab

Patients will receive the following treatment until meeting one of the criteria in [Section 7.5](#).

Cycles 1-4

Agent	Dose	Route	Day	Schedule*
Nivolumab	1 mg/kg	IV over 30 mins	1	q 21 days for 4 cycles only.
Ipilimumab**	3 mg/kg	IV over 90 mins	1	q 21 days for 4 cycles only

* Note: 1 cycle = 21 days

**Ipilimumab to start 30 minutes after the end of nivolumab infusion.

Cycles 5+

Agent	Dose	Route	Day
Nivolumab	480 mg	IV over 30 mins	1 of every cycle

Note: 1 cycle = 28 days

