7.4 Full CDUS Reporting Requirement

Because this study contains an investigational drug for which CTEP holds the IND, it falls under CTEP requirements for full reporting. This involves required submission of cycle-specific toxicity and dose information (see [Section 14.4](#), the **S1616** Treatment Form, and the **S1616** Adverse Event Form).

A cycle is defined as:

- Arm 1: 21 days
- Arm 2: 21 days for first 4 cycles; 28 days for Cycles 5+

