 - Hospitalization for \leq Grade 2 adverse events where the primary reason for hospitalization is to expedite the clinical work-up.
 - Patients with the following conditions where in the treating investigator's opinion continuing study drug administration is justified based on the potential for continued clinical benefit:
 - Patients treated with systemic steroids for less than 2 weeks without evidence of autoimmune disease requiring steroids treatment
 - Grade 2 skin rash treated with topical steroids for less than 4 weeks
 - Grade 2 ocular toxicity that has completely responded to topical therapy within 4 weeks
 - Endocrinopathies where clinical symptoms are controlled with appropriate hormone replacement therapy. **Note:** Ipilimumab may not be restarted while the patient is being treated with systemic corticosteroids except for patients on stable doses of hormone replacement therapy such as hydrocortisone.
- e. Allowance for ipilimumab dose delay
- In general, patients who meet criteria to resume ipilimumab will also have met criteria to resume nivolumab with ipilimumab, so it should be feasible to synchronize dosing of both drugs when resuming ipilimumab. In order to facilitate this, the dosing calendar days of nivolumab and ipilimumab may be adjusted within a +/- 5 day window, as long as consecutive nivolumab doses are given at least 12 calendar days apart.
 - If an ipilimumab dose is delayed beyond 6 weeks from the prior ipilimumab dose, then subsequent nivolumab doses should be rescheduled to maintain at least a 3-week interval between consecutive ipilimumab doses.

- Dosing delays to manage drug-related adverse events, such as prolonged steroid tapers, are allowed. Disease assessments should continue as per protocol even if dosing is delayed.
- Dosing delays resulting in no ipilimumab dosing for > 6 weeks that occur for non-drug-related reasons may be allowed if approved by the Study Chairs. Disease assessments should continue as per protocol even if dosing is delayed.
- In event of any Grade 2 adverse event experienced while on combination nivolumab plus ipilimumab therapy, patient may resume treatment/may be continued on nivolumab monotherapy alone, at the discretion of the treating investigator
- Ipilimumab will not be given as monotherapy for Arm 2.

NOTE: If adverse events result in permanent discontinuation of ipilimumab, then subsequently manage dose delays under Management/Next Dose for nivolumab alone

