8.4 Dose Delay Criteria for Nivolumab in Combination with Ipilimumab (Arm 2)

Dose modifications for nivolumab in combination with ipilimumab by adverse event type are detailed in [Table 8.1](#). General considerations for dose modifications are as follows.

For the initial induction period, patients with Grade 2 or 3 events requiring discontinuation of treatment with the combination may consider continuing treatment with single agent nivolumab when the event resolves to baseline. However, patients with renal, CNS, or pulmonary toxicity must be removed from study.

- a. In addition to the AEs identified in the table below, ipilimumab and nivolumab dose should be delayed for any AE, laboratory abnormality or inter-current illness which, in the judgment of the treating investigator, warrants delaying the dose of study medication.
- b. Patients requiring a delay of > 6 weeks or who experience immune-related toxicity with inability to decrease prednisone ≤ 10 mg PO daily must go off protocol therapy entirely.
- c. Patients who received systemic corticosteroids for management of any drug-related immunologic toxicity must be off corticosteroids or have tapered down to an equivalent dose of prednisone 10 mg/day.
- d. Nivolumab monotherapy may be continued at treating investigator discretion if there is evidence of clinical benefit. In this event, patient will continue nivolumab until AE is resolved and ipilimumab may be re-started or if ipilimumab is permanently discontinued (in congruence with guidelines in table below), then patient will continue nivolumab alone until cycles are completed. At completion of 4 cycles, patient may continue on nivolumab alone, as per protocol. If ipilimumab is permanently discontinued prior to receipt of 4 doses, nivolumab dosing should remain at the Cycle 1-4 dosing (1 mg/kg every 2 weeks) until completion of Cycle 4 and should then switch to Cycle 5+ dosing (480 mg every 4 weeks).

Table 8.1 Dose Modification for Related Adverse Events

Treatment-related Adverse Event	Grade of Event	Nivolumab and/or Ipilimumab
Nausea	≤ Grade 1	No dose modification
	Grade 2	Hold until ≤ Grade 1 OR baseline (exceptions as noted below) ¹
	Grade 3	Off protocol therapy (exceptions as noted below) ¹
	Grade 4	Off protocol therapy
*Patients requiring a delay of >2 weeks must go off protocol therapy.		
Recommended management: antiemetics.		
Diarrhea (immune-related enterocolitis)	≤ Grade 1	No dose modification

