- S CT or MRI of the chest, abdomen, and pelvis should be performed at baseline and all subsequent assessments. Additionally, for patients with known assessable scalp or neck disease, a CT or of the head/face/neck should be performed at baseline and all subsequent assessments. Patients with known assessable extremity disease should have the affected extremity also measured by CT or MRI at baseline and all subsequent visits. Patients with a history of central nervous system metastases must have MRI of the brain at baseline and at all subsequent assessments.
- T Select sites will, at each prospective biopsy timepoint, obtain additional cores. See [Section 15.1c.4](#) for details.

9.2 Arm 2: Cycles 1 through 4 (see [Section 9.3](#) for Arm 1 Cycles 5+)

	Pre-registration G	Cycle (1 cycle = 21 days)											
		1			2			3			4		
		Week ^K											
		1	2	3	4	5	6	7	8	9	10	11	12
PHYSICAL													
History and physical exam	X	X ^L		X			X			X			
Weight and performance status ^N	X	X ^L		X			X			X			
Toxicity notation		X		X			X			X			
Baseline abnormalities		X											
Disease assessments	X												X ^M
Biopsy ^A		X				X							
LABORATORY													
ANC, platelets, and hemoglobin	X	X ^L		X			X			X			
AST, ALT, and total bilirubin	X	X ^L		X			X			X			
Serum creatinine	X	X ^L		X			X			X			
Pregnancy test	X ^H												
Creatinine phosphokinase (CPK), Troponin, and Cardiology consultation ^B	X												
CD4	X ^J												
TSH, Free T4, Free T3 ^C		X		X			X			X			

Calendar continued on next page. Click here for [footnotes](#).

	Pre-registration ^G	Cycle (1 cycle = 21 days)											
		1			2			3			4		
		Week ^K											
		1	2	3	4	5	6	7	8	9	10	11	12
X-RAYS AND SCANS													
MRI or CT for disease assessment ^O	X												X ^M
Electrocardiogram (ECG) and Echocardiogram (Echo) ^D	X												
SPECIMEN SUBMISSION													
Archival tissue ^E		X											
Tissue block or slides from biopsy		X				X							
Blood ^F		X				X							
Fresh Frozen Tissue from biopsy ^P						X							
TREATMENT													
Nivolumab 1 mg/kg		X			X			X			X		
Ipilimumab		X			X			X			X		

Click here for [footnotes](#).

Note: Forms are found on the protocol abstract page of the SWOG website (www.swog.org). The schedule for submission of these forms is listed in [Section 14.0](#)

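### Section 8.4d states the Arm 2 Cycle 1-4 nivolumab interval as 2 weeks, but the treatment plan, cycle definition and study calendar all set 21 days

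*Combined protocol and SAP*

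**What the plan says.** Section 8.4d applies "If ipilimumab is permanently discontinued prior to receipt of 4 doses". For those patients it instructs that "nivolumab dosing should remain at the Cycle 1-4 dosing (1 mg/kg every 2 weeks) until completion of Cycle 4", followed by a switch to 480 mg every 4 weeks from Cycle 5.

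The Cycle 1-4 schedule is set in three other places:

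- Section 7.3 lists nivolumab 1 mg/kg on Day 1, "q 21 days for 4 cycles only".
- Section 7.4 defines cycle length as "Arm 2: 21 days for first 4 cycles; 28 days for Cycles 5" onward.
- Calendar 9.2 is headed "Cycle (1 cycle = 21 days" and marks nivolumab 1 mg/kg at Weeks 1, 4, 7 and 10, on the same visits as ipilimumab.

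Two conditions in Section 8.4 limit who continues on nivolumab alone. After Grade 2 or 3 events, patients "may consider continuing treatment with single agent nivolumab when the event resolves to baseline". Item d adds: "Nivolumab monotherapy may be continued at treating investigator discretion if there is evidence of clinical benefit".

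**The concern.** Item d is the rule a site consults once ipilimumab has been stopped, and the parenthesis is the only induction interval it gives. It presents 14 days as the existing schedule, when the existing schedule is 21 days.

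Two sites could therefore treat the same patient differently: one every 14 days from 8.4d, the other every 21 days from 7.3. The faster schedule would go to patients recovering from toxicity that ended the combination. The only stated minimum gap between nivolumab doses, in Section 8.3e, allows adjustment "as long as consecutive nivolumab doses are given at least 12 calendar days apart". A 14-day interval satisfies it.

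**Working it through.** No power or alpha formula applies. The check is a comparison of sections, followed by schedule arithmetic.

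**Is 14 days obtainable from any other section?** Sections 7.3 and 7.4 give 4 cycles × 21 days = 84 days, with doses on Days 1, 22, 43 and 64. These fall in Weeks 1, 4, 7 and 10, as calendar 9.2 shows, and Cycle 5 starts on Day 85 (Week 13), as in calendar 9.3. Nothing yields 14 days. The other parenthesis in the same sentence, 480 mg every 4 weeks, does agree with 7.3.

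**Could it be a deliberate monotherapy schedule?** No. The sentence tells sites to stay on the Cycle 1-4 dosing, so it restates 7.3 and restates it wrongly.

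**Dose rate**

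- As written in 8.4d: 1 mg/kg ÷ 2 weeks = 0.500 mg/kg/week.
- As planned in 7.3: 1 mg/kg ÷ 3 weeks = 0.333 mg/kg/week.
- Ratio: 0.500 / 0.333 = 1.5.

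**Dose counts to Day 84, no hold, every 14 days from the last combination dose (planned total: 4)**

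| Combination doses given | Nivolumab days | Total |
|---|---|---|
| 1 | 1, 15, 29, 43, 57, 71 | 6 |
| 2 | 1, 22, 36, 50, 64, 78 | 6 |
| 3 | 1, 22, 43, 57, 71 | 5 |

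If dosing restarts at the next scheduled visit instead, the totals are 6, 5 and 5. These are upper bounds, because they need more than one dose in some cycles.

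**Dose counts with a hold.** The hold runs from the next scheduled dose, and Day 84 is kept as a fixed end. Each cell gives the total at 14-day versus 21-day dosing.

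| Combination doses given | 14-day hold | 21-day hold | 42-day hold |
|---|---|---|---|
| 1 | 5 vs 4 | 4 vs 3 | 3 vs 2 |
| 2 | 4 vs 4 | 4 vs 3 | 2 vs 2 |
| 3 | 4 vs 4 | 3 vs 3 | 3 vs 3 |

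The excess is 0 or 1 dose.

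**If a site keeps to four doses in total.** The count is then right but the doses come early. The fourth falls at the earliest on Day 1 + 3×14 = 43, Day 22 + 2×14 = 50, or Day 43 + 14 = 57, after one, two or three combination doses respectively. The planned day is 64. With restart at the next scheduled visit, the days are 50, 57 and 64.

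**Context from Cycle 5 on.** 480 mg ÷ 4 weeks = 120 mg/week. At assumed body weights of 60 and 100 kg this is 2.0 and 1.2 mg/kg/week, which is 4.0 and 2.4 times the erroneous 0.50.

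**The case against.** The strongest reply is that the text largely corrects itself. The operative instruction is to stay on a dosing defined elsewhere at 21 days. To dose every 14 days, a site would have to override that instruction, the Day 1 and four-cycle limits in 7.3, and the four dosing columns of calendar 9.2. Section 8.7 requires liver tests before each dose, and the calendar has no 14-day visit grid to support that. This shows which interval was intended. It does not make the written interval right, and a reader who misses the conflict has only the wrong number in front of them.

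Other points bear on weight, and several stand:

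- The hold scenarios assume a fixed 84-day calendar. Footnote K of calendar 9.2 counts weeks only for patients without delays, and 8.4d runs to the end of Cycle 4, not to Day 84. The rate ratio is the firmer figure.
- Table 8.1 takes most Grade 3 events off protocol therapy, and does the same for delays over 2 weeks for nausea, diarrhea, vomiting and neutropenia. The longer holds therefore do not arise for those events. Conversely, Section 8.3e lets patients with Grade 2 events continue nivolumab alone at the investigator's discretion, without the clinical-benefit condition.
- The 12-day minimum in 8.3e serves to resynchronise the two drugs and is compatible with 21-day dosing: shifts of +5 and -5 days would otherwise leave 21 - 10 = 11 days. It is not evidence of an intended 2-week schedule. It only fails to block one.
- No harm is demonstrated, since the erroneous rate is below the rate the same patients would later receive.
- The pages carry a closure stamp whose meaning is not stated. If it means accrual had ended, few patients may still have been in induction, and the practical value would lie in clarifying the text and checking dosing records of patients who stopped ipilimumab early.

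**Conclusion.** The concern holds. The interval in 8.4d contradicts Sections 7.3 and 7.4 and calendar 9.2, and nothing in the current text corrects it. Followed as written, it gives 1.5 times the planned induction dose rate. In doses, that is at most 2 extra over 84 days with no hold, and 0 or 1 extra after holds of 14 to 42 days if the 84-day window is fixed.

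The number of patients affected cannot be derived from the protocol. No endpoint, alpha, power or sample-size figure changes. It should be fixed because it is a wrong drug interval in an operative toxicity rule; it does not threaten the validity of the trial.

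**What to change.** In Section 8.4d, replace the 2-week interval in the parenthesis with 1 mg/kg every 3 weeks (21 days). Nothing else needs to change: Sections 7.3 and 7.4 and calendar 9.2 already agree with each other. The cost is one phrase by amendment, with no added patients or procedures and no change to the analysis.

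### Section 8.4d gives the Arm 2 Cycle 1-4 nivolumab interval as 2 weeks, while Sections 7.3, 7.4 and calendar 9.2 make it 3 weeks

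*Combined protocol and SAP*

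**What the plan says.** Section 8.4d covers Arm 2 patients who permanently stop ipilimumab before receiving four doses. It instructs that "nivolumab dosing should remain at the Cycle 1-4 dosing (1 mg/kg every 2 weeks) until completion of Cycle 4", followed by a switch to the Cycle 5+ dosing of "480 mg every 4 weeks".

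Three other places define the Cycle 1-4 schedule:

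- Section 7.3 lists nivolumab 1 mg/kg on Day 1, "q 21 days for 4 cycles only".
- Section 7.4 defines the cycle length as "Arm 2: 21 days for first 4 cycles; 28 days for Cycles 5" and later. The same section calls for "required submission of cycle-specific toxicity and dose information".
- Calendar 9.2 uses 21-day cycles, and its row for "Nivolumab 1 mg/kg" is marked at Weeks 1, 4, 7 and 10 only.

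No place outside 8.4d gives a 2-weekly nivolumab schedule.

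**The concern.** Section 8.4d is the specific instruction for this situation, so a careful site may well follow it over the general treatment table. Another site may follow Section 7.3. Each would depart from the other section, and no rule in the documents says which one prevails when they conflict. Patients in the same arm and situation could then be dosed every 14 or every 21 days.

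Three things are at stake:

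- **Exposure.** The nivolumab rate after ipilimumab stops would be half as high again as planned, in patients who have just had toxicity serious enough to end ipilimumab.
- **Reporting.** Dose and toxicity are reported by cycle. Fourteen-day dosing does not fit a 21-day cycle built around one Day 1 dose.
- **Monitoring.** Section 8.7 requires transaminases and bilirubin before each dose of either drug. Calendar 9.2 schedules laboratory tests only about every 3 weeks in Cycles 1-4.

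**Working it through.** The plan gives no figure to reproduce here. The check compares the texts and counts doses.

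**Inputs**

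- 8.4d: 1 mg/kg every 14 days until Cycle 4 is complete.
- 7.3, 7.4 and 9.2: 1 mg/kg every 21 days for 4 cycles, so Cycles 1-4 last 4 x 21 = 84 days and the planned doses fall on days 1, 22, 43 and 64.
- 7.3 and 8.4d: 480 mg every 4 weeks from Cycle 5.
- 11.1: 63 patients in the combination arm.

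**Is 2 weeks a deliberate new schedule?** The wording of 8.4d points the other way. It tells the patient to stay on a dosing that it names as that of Cycles 1-4, so no change of interval is meant. The other half of the sentence, the Cycle 5+ dosing, agrees with 7.3 and 9.3. One number is out of line.

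**Dose rate.** 1/2 = 0.50 mg/kg/week against 1/3 = 0.33 mg/kg/week; the ratio is 3/2 = 1.5.

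**Dose counts to day 84, no dose held.** Nivolumab is given every 14 days after the last ipilimumab dose:

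| Ipilimumab stops after | 8.4d read literally | Doses | Planned |
|---|---|---|---|
| dose 1 | days 1, 15, 29, 43, 57, 71 | 6 | 4 |
| dose 2 | days 1, 22, 36, 50, 64, 78 | 6 | 4 |
| dose 3 | days 1, 22, 43, 57, 71 | 5 | 4 |

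In the first row, Cycle 1 (days 1-21) and Cycle 3 (days 43-63) each hold two doses. Days 29 and 71 fall in Weeks 5 and 11, where calendar 9.2 shows no laboratory tests or toxicity check.

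**Dose counts with one nivolumab visit skipped.** The first nivolumab-alone dose then comes 42 days after the last combined dose under both readings:

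| Ipilimumab stops after | Every 14 days | Every 21 days |
|---|---|---|
| dose 1 | days 1, 43, 57, 71 (4) | days 1, 43, 64 (3) |
| dose 2 | days 1, 22, 64, 78 (4) | days 1, 22, 64 (3) |
| dose 3 | days 1, 22, 43 (3) | days 1, 22, 43 (3) |

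**Scale against Cycle 5+.** 480/4 = 120 mg/week. At assumed weights of 60, 80 and 120 kg this is 2.0, 1.5 and 1.0 mg/kg/week. The faster rate of 0.50 is therefore 25%, 33% and 50% of the rate the patient moves to next.

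**Patients affected.** The documents give no figure. If 10% to 40% of the combination arm stop ipilimumab early and continue nivolumab (an assumption), the range is 0.10 x 63 = 6.3 to 0.40 x 63 = 25.2, or about 6 to 25 patients.

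**The case against.** The strongest reply is that this is an obvious slip that readers would resolve correctly. Section 3.2d sends the reader to Section 7.0 for nivolumab dosing, and 8.4d itself refers back to the Cycle 1-4 dosing. Both favor 3 weeks. This is good evidence of what was intended, but it is not a rule of precedence, and it does not stop a site from following the explicit interval in the section written for its patient. Section 8.3e also allows consecutive nivolumab doses as close as 12 days apart in a related setting. That is only a minimum spacing, but it makes 14 days look permissible.

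A second reply is that 6 doses against 4 is an extreme case. This stands in part. Section 8.4 allows nivolumab alone "when the event resolves to baseline", so a dose on day 15 would need the event to arise and clear within 14 days. With one skipped visit the excess is one dose or none. If completion of Cycle 4 were counted by doses instead of days, both readings would give 4 doses. Without a hold, the fourth would then come 21, 14 or 7 days early (day 43, 50 or 57 instead of 64) after a stop at dose 1, 2 or 3, and the move to 480 mg would follow sooner.

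The recovery condition is only partly reassuring. Section 8.4d also has nivolumab continue while an event is still resolving, and 8.3e leaves continuation after a Grade 2 event to the investigator.

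It is also fair that Table 8.1 takes many Grade 3 events off protocol therapy altogether. That narrows the group affected and is one reason to treat the patient range as no more than an assumption.

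**Conclusion.** The concern holds. The interval in 8.4d contradicts 7.3, 7.4 and 9.2, and its own wording shows that no change of schedule was meant. Read literally, it raises the nivolumab rate 1.5 times after ipilimumab stops. The excess by day 84 is one or two doses with no hold, and one or none with one skipped visit. These counts assume that Cycle 4 ends on day 84.

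The clinical effect is modest: this is nivolumab alone, at a rate below that of Cycle 5+ for the weights considered. Nothing in the sample size, power or alpha of Section 11 changes. It should still be corrected, because it is a wrong number in an operative dosing rule and it blurs what counts as a dosing deviation.

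**What to change.** In Section 8.4d, change the interval in the parenthesis from every 2 weeks to every 3 weeks, keeping 1 mg/kg. Doses then fall on days 1, 22, 43 and 64 when none is held, in agreement with 7.3, 7.4 and 9.2. The cost is one number; sample size, power, alpha and the visit schedule stay as they are. Page stamps show the study as closed in 2020, so for patients already treated the correction mainly settles how deviations are classified and dose data are read.

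An optional and separate wording change concerns Section 8.3e, which places combination rules under the Arm 1 heading and says that "subsequent nivolumab doses should be rescheduled to maintain at least a 3-week interval between consecutive ipilimumab doses". Those rules could move to 8.4. The sentence could then say that later same-day ipilimumab and nivolumab doses are rescheduled so that ipilimumab doses stay at least 3 weeks apart. The main correction does not depend on it.

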8.5 Treatment of Infusion Reactions Associated with Ipilimumab and/or Nivolumab

Since ipilimumab contains only human protein sequences, and since nivolumab is a fully human monoclonal antibody, it is less likely that any allergic reaction will be seen in patients receiving these agents. However, it is possible that infusion of ipilimumab or nivolumab will induce a cytokine release syndrome that could be evidenced by fever, chills, rigors, rash, pruritus, hypotension, hypertension, bronchospasm, or other symptoms. No prophylactic pre-medication should be given unless indicated by previous experience in an individual patient. Reactions should be treated based upon the following recommendations.

- For mild symptoms (e.g., localized cutaneous reactions such as mild pruritus, flushing, rash):
 - Decrease the rate of infusion until recovery from symptoms, remain at bedside and monitor patient.
 - Complete the infusion at the initial planned rate.
 - Diphenhydramine 50 mg IV may be administered at the discretion of the treating physician and patients may receive additional doses with close monitoring.
 - Premedication with diphenhydramine may be given at the discretion of the investigator for subsequent doses.

- For moderate symptoms (any symptom not listed above [mild symptoms] or below [severe symptoms] such as generalized pruritus, flushing, rash, dyspnea, hypotension with systolic BP >80 mmHg):
 - Interrupt infusion of offending agent.
 - Administer diphenhydramine 50 mg IV.
 - Monitor patient closely until resolution of symptoms.
 - Corticosteroids may abrogate any beneficial immunologic effect, but may be administered at the discretion of the treating physician.
 - Resume infusion after recovery of symptoms.
 - At the discretion of the treating physician, infusion may be resumed at *one half the initial infusion rate, then increased incrementally to the initial infusion rate.*
 - If symptoms develop after resumption of the infusion, the infusion should be discontinued and no additional ipilimumab or nivolumab should be administered that day.
 - The next dose will be administered at its next scheduled time and may be given with pre-medication (diphenhydramine and acetaminophen) and careful monitoring, following the same treatment guidelines outlined above.
 - At the discretion of the treating physician additional oral or IV antihistamine may be administered prior to dosing.
- For severe symptoms (e.g., any reaction such as bronchospasm, generalized urticaria, systolic blood pressure < 80 mm Hg, or angioedema):
 - Immediately discontinue infusion, and disconnect infusion tubing from the patient.
 - Consider bronchodilators, epinephrine 1 mg IV or subcutaneously, and/or diphenhydramine 50 mg IV, with solumedrol 100 mg IV, as needed.
 - Patients should be monitored until the investigator is comfortable that the symptoms will not recur.
 - No further ipilimumab (if related to ipilimumab) or nivolumab (if related to nivolumab) will be administered.

